- *Each study site to describe the source population and definition of the study cohort Each study site to specify the target groups for which influenza vaccination is recommended, which vaccines are used in the database catchment area, and how the choice of vaccine brand happens*

Study period

The study follow-up will start before the seasonal influenza vaccine is available and before the influenza virus circulation begins in the country/region, to ensure that all vaccinations and all outcomes in the defined cohort are captured. If only aggregated data will be collected that does not allow the shortening of the study subjects' follow-up as part of the statistical analysis, the follow-up may be restricted to the time the vaccine first becomes available or the virus circulation starts, whichever occurs first. The study period will finish at the end of the influenza season.

- *Each study site to specify the study period: the definition of the beginning and end of the study period*
- *Each study site to specify the early, middle and end of the influenza epidemic at the study site according to the information provided by the local influenza surveillance system.*

For the pooled analysis, a harmonised minimum period will be defined (e.g. from week 40 till week 20), but if needed, it will be extended to fully cover the vaccination campaign and the epidemic in each study site. Definition of shorter time periods (e.g. early, middle and end season) will be developed to take into account differences in influenza activity over time and probable development of immunity in unvaccinated population through encounters with the circulating viruses

For addressing the secondary objective of estimating influenza vaccine effectiveness over several seasons, multiple study periods will be combined. If possible, the information from the local surveillance systems of major circulating strains in the study regions will be considered in the analysis. The details of the analysis will be described in the generic study site level SAP.

Study population and follow-up

Cohort of interest

The study cohort comprises the characterised by place of residence, or catchment population of a health care service providing the relevant information for the analyses. The databases may also be characterised by or restricted to e.g. age, or medical, physiological or occupational conditions (e.g. pregnancy, health care workers, other risk/target groups).

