- *Each study site to specify the data checking and cleaning process*

Statistical analysis

This section describes the main principles for the study site level analysis. The statistical analyses are attempted to be harmonised between the study sites, to optimise the numbers of variables to be used in the adjustment and the heterogeneity/homogeneity between the study sites. After analysing the characteristics and structure of the databases used in participating study sites, a generic site level Statistical Analysis Plan (SAP) will be provided, including guidelines for harmonisation, with details/alternatives for defining the variables. The generic site level SAP will be updated annually, and attached as an Annex 2 to the generic protocols. Details on the site-specific analyses will be provided in the site-specific Statistical Analysis Plans (SAPs), attached as Annexes of the site-specific protocols. Information on the two-stage pooling of data from several study sites is provided in the DRIVE D4.4: “*Generic statistical analysis plan; combining information on influenza vaccine effectiveness across study sites.*” Based on the D4.4, season-specific SAPs for pooling data across study sites will be written. The season-specific SAP is expected to be modified each season to reflect the specificities of the season’s influenza epidemic as well as changes in participating study sites and data availability.

Individual follow-up

The follow-up of an individual belonging to the defined study cohort starts at a fixed time point at the start of the study period, and the follow-up continues until the first occurrence of the defined outcome, until another event leading to right-censoring as defined below, or until the end of the study period, whichever comes first.

Study subjects are right-censored, i.e. their individual follow-up ends, after the first occurrence of the outcome defined for the analysis in question. Other reasons for right-censoring have to be defined according to data availability and harmonised between the study sites: death, moving out of from the cohort catchment area, administration of an influenza vaccine of a type or brand other than the exposure defined for the analysis, having and influenza infection caused by an influenza virus type/subtype/lineage other than the one defined as the outcome for the analysis.

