The analysis must be conducted for each exposure and outcome of interest separately. Confounder-adjusted brand-specific, type specific or overall IVE estimates will be obtained from multivariable regression models, regressing the health outcomes of interest on exposure status, age, sex and the confounders of interest. In case of effect modifiers, an interaction term between exposure and the effect modifier will be included in the regression model or stratified regression analyses will be performed.

Depending on the type of data available, the analytical method(s) will be described in the generic study site level SAP and in a study-specific SAP before the start of the study period. For the outcome of interest, irrespective of its type, multivariable logistic regression will be used, if only the number of events as vaccinated and unvaccinated by number of subjects vaccinated and unvaccinated at the end of the follow-up is known. If the number of events by person time and vaccination status can be assessed, Poisson regression will be used. In case of time-to-event data, Cox regression (proportional hazards) will be used.

Missing data

The cohort should be defined so that the missing data is minimised: the cohort should cover all subjects targeted, especially for the vaccination, and only those subjects. Especially the outcome should be caught non-differentially, i.e. similarly for vaccinated and unvaccinated (see section Study population and follow-up; Cohort of interest). Missing data for events occurring during the follow-up is not available, since 'no record' means by definition 'no event' (unless also the negative

outcome information, e.g. negative influenza tests are available, when a nested case control analysis could be performed).

Missing data may be present, if historical data for background factors at start of the follow-up is not available, e.g. if the subject has moved into the attachment area of the database recently, or it is incomplete, e.g. only part of the databases used in defining the different background factors are available. This subcohort may be excluded from the adjusted analyses.

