Annex 1: The dataset

Annex 1 defines the data elements to be used for estimating brand-specific VE in a population based cohort study using secondary data from pre-existing databases. The minimum dataset is marked with an asterisk(*), but preferably the most important covariates to adjust for will be included. According to these data elements, the analysis database will be developed to include the defined outcome events by person months vaccinated, (partially vaccinated) and unvaccinated, considering the events leading to right-censoring, and the covariates needed for adjustment or stratification.

The database may alternatively be structured for aggregated data, initially based on these data elements.

Instructions for harmonisation of the variables and the structure of analysis database will be provided in the generic study site level Statistical Analysis Plan (SAP), Annex 2. Season-specific updates in Annex 2 will be implemented to Annex 1, if needed.

DRIVE – The dataset for estimating VE in a population based cohort study using secondary data from pre-existing databases. The minimum data set is marked with an asterisk(*)�.

	Variable	Description	Format	Values and coding	Example
General	idcountry*	Country code defined in ISO 3166-1 alpha-2	2 letters text		Finland
	id*	Patient or aggregate identification number	Unique integer		12345678
	cohort*	Cohort name	Text		THL
	region*	Region name	Text		Pirkanmaa
	dataset*	Data set name	text		Elderly
	sex*	Sex	Numeric (Binary)	0=Female 1=Male	0
	dob* (alternatively age)	Date of birth or age at the start of the follow-up (children: months; adults:years)	dd/mm/yyyy	Date between the date of birth of the oldest and youngest study subject	01/01/1960

The follow-up	startdate*	Date of the start of the study period	dd/mm/yyyy	Date within the study period	30/12/2017
	enddate*	Date of the end of the study period ^a	dd/mm/yyyy	Date within the study period	30/12/2017
	middledate	Date separating the early and the middle epidemic season	dd/mm/yyyy	Date within the study period	30/12/2017
	latedate	Date separating the middle and the end epidemic season	dd/mm/yyyy	Date within the study period	30/12/2017
	death*	Died during the follow-up	Numeric (Binary)	0=No 1=Yes	1
	deathdate*	Date of death ^a	dd/mm/yyyy	Date within the study period	30/12/2017
	moved(*)	Moved out of the cohort catchment area during the follow-up	Numeric (Binary)	0=No 1=Yes	1

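### Poisson analysis of person-time that begins before virus circulation names no calendar-time term; followed as written, it biases VE downward

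*Combined protocol and SAP*

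**What the plan says.** Four rules act together.

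- **Start of follow-up.** The Study period section sets an early start: "The study follow-up will start before the seasonal influenza vaccine is available and before the influenza virus circulation begins in the country/region". The section on individual follow-up makes it common to all: "The follow-up of an individual belonging to the defined study cohort starts at a fixed time point at the start of the study period". For pooling, "a harmonised minimum period will be defined (e.g. from week 40 till week 20" and extendable.
- **Status.** Under Definition of vaccination status, a subject is unvaccinated up to the first record of the season, partially vaccinated for 14 days, then vaccinated. Young children not previously fully vaccinated follow a two-dose rule for injectable vaccine. Individual follow-up lets one subject contribute person-time to each state.
- **Model.** Measure of effect: "If the number of events by person time and vaccination status can be assessed, Poisson regression will be used". Adjusted estimates come from "regressing the health outcomes of interest on exposure status, age, sex and the confounders of interest". The list of potential confounders and effect modifiers does not contain calendar time.
- **Data layout.** Annex 1 plans an analysis database holding "the defined outcome events by person months vaccinated, (partially vaccinated) and unvaccinated". It adds right-censoring events and covariates for adjustment or stratification, and names no calendar key.

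Study period also has three related provisions. For aggregated data, "the follow-up may be restricted to the time the vaccine first becomes available or the virus circulation starts, whichever occurs first". Shortening of follow-up in the analysis is mentioned without a rule. Early, middle and end periods are still to be developed to reflect influenza activity.

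**The concern.** Before the virus circulates nobody can become a laboratory-confirmed case, yet those weeks count as person-time. Early in follow-up nearly everyone is unvaccinated, including people vaccinated later. By the epidemic many have moved to the vaccinated group. The unvaccinated denominator is therefore loaded with risk-free time, and a model without calendar time reads this as a low rate in the unvaccinated. This is confounding by calendar time. Larger samples only narrow the interval around the wrong value.

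It touches the primary objective, brand-specific VE, because every brand is compared with the same unvaccinated person-time. Cox regression timed from the common start date compares people on the same calendar day, so weeks without events contribute nothing. Poisson and Cox sites could therefore differ in pooling only because of the form of their data.

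**Working it through.** **The plan's own figure.** The documents give no figure for this bias. The nearest is the precision claim: 5000 subjects, true VE 50%, attack rate 5%, lower 95% limit above 25% for coverage above 20%. Annex 3, formula (3), at 50% coverage has A1 = 62.5, A0 = 125, N1 = N0 = 2500. The standard error is √(0.016 − 0.0004 + 0.008 − 0.0004) = 0.152, so the lower limit is 1 − 0.5·exp(1.96 × 0.152) = 32.6%. At coverage 20%, 21% and 70% it is 24.7%, 25.3% and 32.3%. The claim reproduces. It concerns sampling error only.

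**Inputs for the bias.** From the documents: VE 50%, attack rate 5%, coverage 20/50/70%, the example window of weeks 40 to 20 (33 weeks), and the 14-day partial period. Assumed, because the documents do not give them: timing of uptake and of the epidemic.

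**Formula.** Let T be weeks of follow-up, u the mean weeks from start to vaccination among vaccinees, v = T − u − 2 their mean fully vaccinated weeks, g the coverage and λ the epidemic risk. For a rare outcome, with uptake finished before circulation:

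- unvaccinated rate = (1 − g)λ / [(1 − g)T + g·u]
- vaccinated rate = 0.5·λ / v
- crude rate ratio = (0.5 / v) × [T + u·g/(1 − g)]

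If follow-up began only once everyone due for vaccination was fully vaccinated (no vaccinee time counted as unvaccinated or partial, v = T), the ratio would be 0.5, as it should be.

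**Base timing.** Uptake is uniform from week 42 to the start of week 50 and circulation lasts 14 weeks from week 51. Then T = 33, u = 6, v = 25.

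- g = 0.2: 0.02 × (33 + 1.5) = 0.69, VE 31%
- g = 0.5: 0.02 × (33 + 6) = 0.78, VE 22%
- g = 0.7: 0.02 × (33 + 14) = 0.94, VE 6%

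A day-by-day calculation, which allows for depletion of susceptibles and the partial period, gives 31/22/5%.

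**Other timings** (day-by-day calculation, true VE 50%):

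| Timing | 20% | 50% | 70% |
|---|---|---|---|
| Uptake weeks 40–43, epidemic from week 50 to study end | 41.8 | 39.0 | 34.1 |
| Uptake weeks 40–48, epidemic about weeks 50–14 | 35.1 | 28.5 | 16.6 |
| Uptake weeks 42–50, epidemic about weeks 51–12 | 28.9 | 18.6 | 0.2 |
| As the row above, follow-up from week 36 | 18.4 | 1.8 | −27.8 |

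In the second row at 50% coverage, the unvaccinated hold 80.6% of classified person-time before circulation and 49.8% during the epidemic. With a true VE of 0, the crude estimate runs from −16% to −156% across these timings. A brand with 40% of the vaccines at 50% coverage shows the same crude values as overall VE.

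**With calendar time.** Week strata return 50% throughout; 30-day strata return 46.6% to 50.0%. In a simulated cohort of 400,000 (second row, 50% coverage), Poisson regression gave 28.5% (95% CI 26.0 to 30.9) without a time term and 49.6% (47.8 to 51.3) with week terms.

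**Do the Study period provisions repair it?**

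- Start at vaccine availability, base timing (T = 31, u = 4, v = 25): ratios 0.64, 0.70 and 0.81, so VE 36/30/19%. Better, not repaired.
- Three periods with pre-circulation time falling into the early one: 18% to 47% across the assumed timings that begin at week 40.
- Start at circulation: 50% if uptake has ended. With circulation from week 47 and uptake continuing to week 50 or 52: about 49% to 58%, depending on epidemic shape and coverage.

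**The case against.** The strongest reply is that this is a generic protocol. The analytical methods are to be detailed in the site-level SAP, and Annex 2 says that SAP is still to be developed. The early start is justified by complete capture of vaccinations and outcomes, so it need not be the analysed at-risk window. Study period implies that sites with individual data may shorten follow-up in the analysis, and it recognises that influenza activity varies over time.

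Much of this is fair, and it limits what can be said. A reader might infer that the plan rules out a calendar-time term, or that Annex 1 aggregates by vaccination status alone. Neither follows. The term is unspecified, and Annex 1 allows covariates for adjustment or stratification and lists dates from which calendar time could be built. A reader might also infer bias towards zero; the direction is downward, and it can pass zero. Nor do the documents establish that pooled results will be heterogeneous or that particular brands will look worse. They do not say which sites would use Poisson or Cox, and the pooling SAP is a separate document.

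What remains is that the section stating the main principles names a model and its terms, and that model gives a wrong answer if followed. None of the three provisions is linked to it. The restricted start is optional and takes the earlier of two dates, and the dates separating the epidemic periods are outside the minimum dataset.

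**Conclusion.** The concern holds as a flaw in the stated Poisson analysis. Across the assumed timings at 20% to 70% coverage, the estimate for a true VE of 50% ranges from about 42% down to about 5% or lower, reaching −28% when late uptake, 70% coverage and a week-36 start combine. That is a loss of about 8 to 78 points. The direction rests on the written rules and on uptake taking place largely before the epidemic. The size rests on timing that the documents do not give, so no single figure should be read as the expected bias. A generic SAP still to be written could close the gap, but the principle should be set here because sites will adapt this text. The remedy is cheap and the error affects the primary objective, so it should be corrected before any Poisson estimate is pooled.

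**What to change.** - **Measure of effect and Annex 1:** require events and person-time to be aggregated by calendar week, with calendar month as a minimum that leaves a small residual bias. Require calendar period in the Poisson model as strata or a factor. State that Cox models use calendar time as their time scale. Carry the same rule into Annex 2 when it is written.
- **Study period:** for sites that cannot split time, replace the earlier-of-two-dates rule with a start of at-risk time at local virus circulation, with people already vaccinated entering as vaccinated. Note that this is unbiased only if uptake has essentially ended by then.
- Do not use the pre-circulation weeks as a negative-control period for laboratory-confirmed influenza. With no virus there are no events in either group, and the ratio is undefined.

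Cost: protocol and SAP wording, one more aggregation key, and somewhat larger aggregate tables. The dates of positive tests and of first vaccination are already in the minimum dataset.

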To measure seasonal IVE against medically attended laboratory-confirmed influenza, by vaccine brand, then by vaccine type (e.g. by antigen preparation strategy, number of virus strains, adjuvant; see section *Exposure*), then by overall influenza vaccination.

Secondary objectives

To estimate IVE (brand-specific, type specific and total, if possible) against laboratory-confirmed influenza by:

- age group (children, young adults and elderly; the age groups will be further defined in the generic study site level SAP)
- influenza virus type (A, B) and/or subtype (A/H1N1, A/H3N2) and lineage (B/Victoria, B/Yamagata)
- severity/level of health care required (primary health care, hospitalisation)
- risk groups / target groups for vaccination, e.g
 - pregnant women
 - healthcare workers
 - any chronic condition (see Annex 1 and Annex 2)
 - specific chronic conditions (see Annex 1 and Annex 2)
- time since vaccination
- time window in the epidemic season (early, middle, end)(see section Study period)
- previous influenza vaccinations (one or preferably more previous seasons)

To estimate IVE (brand-specific, type specific and total, if possible) against non-specific outcomes with public health relevance, e.g.

- suspected or diagnosed influenza requiring medical attention (primary care and/or hospitalisation)

- respiratory infection, pneumonia or other respiratory conditions requiring hospitalisation, intensive unit care, or leading to death other non-specific outcomes such as cardiovascular events or deterioration of chronic conditions

To estimate brand-specific, type specific or total IVE against laboratory confirmed influenza and/or unspecific outcomes across several seasons, considering the local circulation of the strains and clades detected by the virus surveillance systems, if possible

The details of the analyses will be prescribed in the generic study site level SAP, updated annually according to the characteristics and structure of data available at the participating study sites

Methods

Study design

In each participating study site, a cohort study using secondary data from existing databases or health care registers (see section *Cohort of interest*). To reach appropriate sample size for assessing brand-specific VE, the data from individual studies will be pooled.

Study setting

The population-based study setting is defined by each study site, based on the available data.

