Multiple imputation methods are rarely used to correct for missing data in cohort studies, but it may be applied for categorical background factors at start of the follow-up, assuming that the missingness does not depend on unobserved variables. A sensitivity analysis may be carried out comparing the IVE estimates based on the multiple imputation approach with the IVE estimates based on a restricted subpopulation with full background data available.

Addressing confounding & bias

Observational influenza vaccine effectiveness studies are prone to several sources of confounding and other types of bias. Please also refer to section *Potential confounders and effect modifiers* and DRIVE D2.2: Systematic review of the sources of confounding, bias and strategies to manage their impact in influenza vaccine effectiveness studies.

- *Negative confounding* refers to biases that reflect the fact that high risk groups (people more likely to develop severe complications) will be more likely to be vaccinated and therefore reduce VE. If negative confounding is present, the VE will be underestimated. Adjustment for potential negative confounding factors documented in the study (e.g. presence of chronic diseases) will minimise negative confounding.
- *Positive confounding* refers to biases that reflect a ‘healthy vaccine effect’. People with a healthy lifestyle will be more likely to accept vaccination, thus leading to an increase of measured VE. Or, similarly, people being in a state of “extreme frailty” will not be offered vaccination. If positive confounding is present, VE will be overestimated.

Thus, methods should be developed to recognise, and if possible, to model both the frailty (e.g. number and severity of underlying conditions) and the healthcare seeking behaviour adequately and to balance possible differences between the vaccinated and the unvaccinated in the study cohort e.g. by applying the propensity score methodology. Propensity score is the probability of being vaccinated given the baseline information. It is estimated as a unique value for each study subject and used in the VE model to adjust for baseline differences between the non-vaccinated and vaccinated, e.g. in quintiles (please, refer also to Annex 2 and DRIVE D7.3).

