dement	Dementia	Numeric (Categorical)	0=No 1=Yes 9999=No information	0

stroke	History of stroke	Numeric (Categorical)	0=No 1=Yes 9999=No information	0
rheumat	Rheumatologic diseases	Numeric (Categorical)	0=No 1=Yes 9999=No information	0
obesity	Obesity	Numeric (Categorical)	0=No 1=Yes 9999=No information	0
chronic1	At least one chronic disease	Numeric (Binary)	0=No 1=Yes 9999=No information	1
chronic5	At least 5 chronic diseases	Numeric (Binary)	0=No 1=Yes 9999=No information	1
Pregnancy and perinatal/congenital risk factors (in children)				
pregnancy	Pregnancy at start of the study period	Numeric (Categorical)	0=No 1=Yes 9999=Not applicable	0
childrisk	Any perinatal or congenital risk factor in children	Numeric (Categorical)	0=No 1=Yes 9999=No information	0

Health care utilisation and propensity score				
nhosp	Number of hospitalisations 12 months prior to the study period	Numeric	≥0 or 9999=No information	2
nphcvisit	Number of outpatient primary health care visits to physician 12 months prior to the study period	Numeric	≥0 or 9999=No information	5
adherence	Adherence in the childhood vaccination program (in children)	Numeric (Categorical)	0=No 1=Low 2= Moderate 3= Complete 9999=No information	3
propensity score	Quintiles of the probability to be vaccinated according to background factors	Numeric	1-5	4
Life style, medications, social and functional status and miscellaneous				
siblings	(In children) Number of siblings living	Numeric	≥0 or 9999=No information	2
bmi	Body Mass Index	Numeric	10 to 55 or 9999=No information	22.4
smoking	Smoking status (parental smoking in children)	Numeric (Categorical)	0=Non-smoker 1=Ex-smoker 2=Smoker 9999=No information	0

dependency	Patient has contract to regular home care or difficulty in at least one category of daily living ^g	Numeric (Categorical)	0=No 1=Yes 9999=Not applicable	0
inst	Institutionalized	Numeric (Categorical)	0=No 1=Yes 9999=No information	0
contra	Contraindication for influenza vaccination	Numeric (Categorical)	0=No 1=Yes 9999=No information	0
sosstatus	Socio-economic status or applicable proxy	Numeric (Categorical)	1=low 2=medium 3= high 9999=No information	2
antiviral	Antiviral use during follow-up	Numeric (Categorical)	0=No 1=Yes 9999=No information	1
statin	Statin use during follow-up	Numeric (Categorical)	0=No 1=Yes 9999=No information	1

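### Where a propensity score is used, the plan describes one that is not tied to a brand, so brand-specific VE adjusted mainly by it can be biased in opposite directions for different brands

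*Combined protocol and SAP*

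**What the plan says.** The primary objective ranks the estimates: VE is measured "by vaccine brand, then by vaccine type", and overall vaccination comes last. Annex 3 compares recipients of the brand of interest with subjects who stay unvaccinated, and the section on individual follow-up censors a subject who receives another brand.

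For adjustment, the Measure of effect section names multivariable regression, "regressing the health outcomes of interest on exposure status, age, sex and the confounders of interest", and adds that "The analysis must be conducted for each exposure and outcome of interest separately".

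The propensity score appears under Addressing confounding & bias. It is an example of how "to balance possible differences between the vaccinated and the unvaccinated in the study cohort e.g. by applying the propensity score methodology". The definition is "Propensity score is the probability of being vaccinated given the baseline information", and the text continues: "It is estimated as a unique value for each study subject and used in the VE model to adjust for baseline differences". Details are left to Annex 2, which is still a placeholder, and to a separate DRIVE deliverable that is not part of these documents.

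Annex 1 holds one row for the score: "Quintiles of the probability to be vaccinated according to background factors", coded 1 to 5. The row has no asterisk, so it lies outside the minimum dataset. The exposure rows in the same table exist separately for each brand and each vaccine type.

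**The concern.** A score for any vaccination makes vaccinees as a whole comparable with the unvaccinated. It makes one brand's recipients comparable with the unvaccinated only if, at a given score, brand choice is unrelated to risk. The protocol does not assume this; under Study setting it asks each site to explain how brands are chosen.

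If one brand goes mainly to frail people, its recipients remain frailer than their comparators within a score quintile, and recipients of the other brand remain healthier. The first brand's VE is then too low and the second's too high. The overall VE stays correct, so checking the overall result would not reveal the problem.

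The score is meant to carry frailty and care-seeking, and the only covariates starred as the minimum for pooling are age and sex. A site that fills the single Annex 1 field and relies on it for frailty could report brand-specific VE that partly reflects who received which brand.

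**Working it through.** The plan states no figure on this point, so there is none to reproduce. The true VE of 50% and the 5% attack rate are the protocol's own planning values. Every other input below is an assumption.

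**1. One stratum of the any-vaccination score.** Take two equal-sized groups with the same probability of vaccination, risk ratio k between them and a mean attack rate of 5% if unvaccinated:

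- r_L = 0.05 × 2/(1 + k), and r_H = k × r_L.
- Brand 1 goes to a share q of high-risk vaccinees and 1 − q of low-risk vaccinees; brand 2 takes the rest.
- VE(brand 1) = 1 − 0.5 × [q r_H + (1 − q) r_L] / 0.05. For brand 2, swap q and 1 − q.

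For k = 2 and q = 0.8, r_L = 0.0333 and r_H = 0.0667:

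- Brand 1: 1 − 0.5 × (0.0533 + 0.0067)/0.05 = 1 − 0.5 × 1.2 = 40%.
- Brand 2: 1 − 0.5 × (0.0133 + 0.0267)/0.05 = 1 − 0.5 × 0.8 = 60%.

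| k | q | Brand 1 | Brand 2 |
|---|---|---|---|
| any | 0.5 | 50% | 50% |
| 1.5 | 0.6 | 48% | 52% |
| 2 | 0.6 | 46.7% | 53.3% |
| 2 | 0.8 | 40% | 60% |
| 3 | 0.8 | 35% | 65% |

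There is no bias when brand choice is unrelated to risk (q = 0.5).

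**2. Quintiles in a simulated cohort of 4 million.** Frail 30%; logit P(any vaccine) = −0.6 + 0.5 × frail + 0.8 × care-seeking score; risk 4%, multiplied by 2 (or 1.5 or 3) if frail and by exp(−0.1 × care-seeking score); true RR 0.5 for both brands. Channelling of 80/20 means that brand X goes to 80% of frail vaccinees and 20% of other vaccinees. The estimate is the Mantel-Haenszel RR over score quintiles, Σ(a₁n₀/n) / Σ(a₀n₁/n).

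| Channelling | Risk ratio if frail | Brand X | Brand Y |
|---|---|---|---|
| 65/35 | 1.5 | 47% | 52.5% |
| 65/35 | 2 | 44% | 55% |
| 80/20 | 2 | 36% | 59% |
| 80/20 | 3 | 30% | 63% |

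Repeat runs move these by a point or two. In the three settings with doubled or tripled risk, quintiles of a score for brand X versus unvaccinated gave 49–51%. The any-vaccination score gave about 50% for overall VE.

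**3. What regression adjustment does.** A second simulation (2 million subjects, Poisson regression) used two binary covariates, labelled age and chronic condition, and one continuous covariate. Brand choice depended on the chronic condition. True VE was 50% for both brands.

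| Adjustment | Brand 1 | Brand 2 | Gap (points) |
|---|---|---|---|
| Any-vaccination quintiles only | 45.4% | 55.5% | 10.1 |
| Same, plus age | 46.7% | 53.8% | 7.1 |
| Same, plus all covariates | 50.0% | 51.2% | 1.2 |
| All covariates, no score | 50.0% | 51.2% | 1.2 |
| Brand-specific quintiles | 49.3% | 51.3% | 2.0 |

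The bias therefore depends on whether the variables that drive brand choice are in the outcome model. Adding age alone leaves most of it.

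**The case against.** A reader might infer that one propensity score adjusts every analysis. The documents do not support that. The score is offered as an example among methods still to be developed, its Annex 1 row is optional, and the stated method is regression for each exposure. Annex 1 lists the likely channelling covariates one by one (chronic conditions, institutionalisation, dependency, hospitalisations). A site that enters them all is protected, as step 3 shows. This part of the objection stands.

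The wording can also be read more kindly. The Exposure section defines a vaccinated person in relation to the vaccine under study, so the score in a brand X analysis could mean the probability of receiving brand X. A unique value per subject may mean only an individual-level value. Annex 2 or the deliverable may settle this. The text is therefore ambiguous, but the ambiguity is not harmless: Annex 1 has exposure fields for each brand and type and a single score field with no such index, and running analyses separately by exposure does not say that the score is re-estimated.

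Finally, the protocol plans no formal test between brands. A reader might infer that it would declare false brand differences; those could arise only from reading separate estimates side by side. Each brand's own VE would still be biased.

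**Conclusion.** The point holds for analyses that use a propensity score as the main carrier of frailty and care-seeking. In that case the score and field as described do not secure balance for the brand-versus-unvaccinated contrast. With a doubled risk in the frail and both brands truly at 50%, the illustrative result is 44% v 55% to 36% v 59%. With weak channelling and a risk ratio of 1.5 it is only 47% v 52.5%.

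These sizes rest on assumed channelling and risk, on reading the score as any vaccination, and on leaving the channelling covariates out of the outcome model. They illustrate the mechanism and do not predict the bias at any site. The point does not show that the plan's main regression analysis is biased. It is a cheap improvement that should be made before sites build the field.

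**What to change.** Under Addressing confounding & bias, state that any propensity score is estimated separately for each exposure contrast: brand X, or type X, versus unvaccinated. A multinomial model over the brands and no vaccination does this in one fit, with the brand X score taken as P(X) / [P(X) + P(unvaccinated)]. It also gives a score to subjects who later receive another brand. They contribute unvaccinated person-time until they are censored and would have no score if the model were fitted only to brand X recipients and the never vaccinated. Require covariate balance to be checked per brand.

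In Annex 1, index the propensity score field by brand and type, as the exposure fields already are, and keep the any-vaccination score for overall VE only.

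The cost is a few sentences and one extra model or score per brand or type, on data already held. The downside is that scores for rare brands will be less stable.
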